6.1.1.3 Disease Progression

The following will be considered disease progression for determination of PFS using the updated response assessment criteria for high-grade gliomas: Response Assessment in Neuro-Oncology (RANO) working group guideline [79].

This study will apply the RANO criteria for high grade gliomas to assess radiographic disease status. These criteria specify assessment of enhancing disease to define progression and response. It is likely that a significant number of subjects eligible for the proposed study will have non-enhancing disease. For subjects without enhancing disease to be eligible for the study, the RANO allowance for FLAIR will be utilized for non-enhancing disease. FLAIR considerations are detailed in the tables below.

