6.1.1.3.1 CRITERIA FOR DETERMINING FIRST PROGRESSION DEPENDING ON TIME FROM INITIAL CHEMORADIOTHERAPY

TABLE 3. RANO CRITERIA FOR DETERMINING FIRST PROGRESSION

First Progression	Definition
Progressive disease <12 weeks after completion of chemoradiotherapy	Progression can only be defined using diagnostic imaging if there is new enhancement outside of the radiation field (beyond the high-dose region or 80% isodose line) or if there is unequivocal evidence of viable tumor on histopathologic sampling (e.g., solid tumor areas [i.e., > 70% tumor cell nuclei in areas], high or progressive increase in MIB-1 proliferation index compared with prior biopsy, or evidence for histologic progression or increased anaplasia in tumor). Note: Given the difficulty of differentiating true progression from pseudoprogression, clinical decline alone, in the absence of radiographic or histologic confirmation of progression, will not be sufficient for definition of progressive disease in the first 12 weeks after completion of concurrent chemoradiotherapy.
Progressive disease ≥ 12 weeks after chemoradiotherapy completion	
 1. New contrast-enhancing lesion outside of radiation field on decreasing, stable, or increasing doses of corticosteroids. 2. Increase by ≥ 25% in the sum of the products of perpendicular diameters between the first post-radiotherapy scan, or a subsequent scan with smaller tumor size, and the scan at 12 weeks or later on stable or increasing doses of corticosteroids. 3. Clinical deterioration not attributable to concurrent medication or comorbid conditions is sufficient to declare progression on current treatment but not for entry onto a clinical trial for recurrence. 4. For patients receiving antiangiogenic therapy, significant increase in T2/FLAIR non-enhancing lesion may also be considered progressive disease. The increased T2/FLAIR must have occurred with the patient on stable or increasing doses of corticosteroids compared with baseline scan or best response after initiation of therapy and not be a result of comorbid events (e.g., effects of radiation therapy, demyelination, ischemic injury, infection, seizures, postoperative changes, or other treatment effects).

6.1.1.3.1.1 CRITERIA FOR RESPONSE ASSESSMENT INCORPORATING MRI AND CLINICAL FACTORS

Criteria for Response Assessment Incorporating MRI and Clinical Factors (Adapted from JCO 2010)

TABLE 4. RESPONSE EVALUATION AFTER A COMPLETE RESECTION

Response	Criteria

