Progression	
Defined by any of the following:
 
 ≥ 25% increase in sum of the products of perpendicular diameters of enhancing lesions compared with the smallest tumor measurement obtained either at baseline (if no decrease) or best response, on stable or increasing doses of corticosteroids*. The absolute increase in any dimension must be at least 5mm when calculating the products. Significant increase in T2/FLAIR non-enhancing lesion on stable or increasing doses of corticosteroids compared with baseline scan or best response after initiation of therapy* not caused by comorbid events (e.g. radiation therapy, demyelination, ischemic injury, infection, seizures, postoperative changes, or other treatment effects). Any new measureable lesion. Clear clinical deterioration not attributable to other causes apart from the tumor (e.g. seizures, medication adverse effects, complications of therapy, cerebrovascular events, infection, and so on) or changes in corticosteroid dose. Failure to return for evaluation as a result of death or deteriorating condition; or clear progression of non-measurable disease.

- All measurable and non-measurable lesions must be assessed using the same techniques as at baseline.

- Abbreviations: MRI, magnetic resonance imaging; FLAIR, fluid-attenuated inversion recovery.
- Stable doses of corticosteroids include patients not on corticosteroids.

The determination of whether to stop treatment due to progression will be based on the investigator's evaluation of the patient's clinical condition. TTFelds treatment will be continued for 24 months or until second progression whichever occurs first unless the patient's clinical condition prohibits this. In the case of radiological progression based on local evaluation, temozolomide treatment will be stopped and a second line treatment chosen instead. The following treatments or any combination of these treatments are considered second line therapy in this protocol:

- Re-operation
- Local radiation therapy
- Second line therapy
- Combination of the above

6.1.1.3.1.2 DISEASE PARAMETERS

Measurable disease: Bi-dimensionally measurable lesions with clearly defined margins by MRI scan. All tumor measurements must be recorded in millimeters (or decimal fractions of centimeters).

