The best overall response is the best response recorded from the start of the treatment until disease progression/recurrence (taking as reference for progressive disease the smallest measurements recorded since the treatment started). The patient's best response assignment will depend on the achievement of both measurement and confirmation criteria.

TABLE 5. SUMMARY OF THE RANO RESPONSE CRITERIA (ADAPTED FROM JCO 2010)

Criterion	CR	PR	SD	PD
T1 gadolinium enhancing disease	None	$\geq 50\%$ ↓	$< 50\%$ ↓ but $< 25\%$ ↑	$\geq 25\%$ ↑*
T2/FLAIR	Stable or ↓	Stable or ↓	Stable or ↓	↑*
New lesion	None	None	None	Present*
Corticosteroids	None	Stable or ↓	Stable or ↓	NA [†]
Clinical status	Stable or ↑	Stable or ↑	Stable or ↑	↓*
Requirement for response	All	All	All	Any*

Abbreviations: RANO, Response Assessment in Neuro-Oncology; CR, complete response; PR, partial response; SD, stable disease; PD, progressive disease; FLAIR, fluid-attenuated inversion recovery; NA, not applicable.

* Progression occurs when this criterion is present.

† Increase in corticosteroids alone will not be taken into account in determining progression in the absence of persistent clinical deterioration.

NOTE: Patients may continue on treatment and remain under close observation and evaluation at 4-8 week intervals if there is uncertainty regarding whether pseudoprogression may be present as determined by the investigators. If subsequent radiographic or clinical assessments suggest that the patient is in fact experiencing progression, then the date of progression should be the time point at which this issue was first raised. Similarly, stable disease may be assigned in cases of presumed “pseudoprogression” associated with decreased steroid use.

6.1.1.3.1.7 DURATION OF RESPONSE

Duration of overall response: The duration of overall response is measured from the time measurement criteria are met for CR or PR (whichever is first recorded) until the first date that recurrent or progressive disease is objectively documented (taking as reference for progressive disease the smallest measurements recorded since the treatment started).

The duration of overall CR is measured from the time measurement criteria are first met for CR until the first date that progressive disease is objectively documented.

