6.1.1.3.2 RESPONSE EVALUATION AFTER A COMPLETE RESECTION

A complete resection will be defined as contiguous contrast-enhancement <10 mm in 2 perpendicular measurements in each of 2 perpendicular planes (i.e., axial and coronal). Because neither the RECIST[80] nor MacDonald [81] criteria are completely appropriate for patients with minimal residual disease, a modified version of these criteria will be used as outlined below.

6.1.1.3.2.1 COMPLETE RESPONSE

Complete disappearance of enhancing tumor on consecutive CT or MRI images at least 1 month apart, and neurologically stable or improved and at the same or a lower steroid dose. To be assigned a status of “Complete Response” as a best overall response, changes in tumor measurements must be confirmed by repeat assessments that should be performed no less than 4 weeks after the criteria for response is first met.

6.1.1.3.2.2 PARTIAL RESPONSE

Partial response is not assessable in patients without sufficient measurable disease.

6.1.1.3.2.3 STABLE DISEASE

Insufficient change to qualify for Complete Response or Progressive disease.

6.1.1.3.2.4 PROGRESSIVE DISEASE

At least a 25% increase in the longest diameter on an axial image of any enhancing tumor on consecutive CT or MRI images with a minimum of ≥ 5 mm of contiguous contrast-enhancement in 2 perpendicular measurements in each of 2 perpendicular planes (i.e., axial and coronal).

6.1.1.3.2.5 NOT ASSESSABLE

Progression has not been documented and one or more sites have not been assessed.

6.1.1.3.2.6 POST-TREATMENT EVALUATION

After treatment termination the patient will be seen at an outpatient clinic for one additional visit within 30 days +/- 7 days. Physical and neurological examination, blood tests (CBC and Biochemistry panel) will be performed during this visit. Patient mortality and adverse events will be documented on the case report forms.

After the post treatment follow up visits, if the patient has not progressed by treatment termination, patient will have contrast-enhanced brain MRI every 3 +/- 1 months for 12 months. Then MRIs every 6 +/- 2 months for 24 months, then yearly +/- 1 month thereafter or until disease progression, whichever comes first.

In case of clinical progression an MRI will be performed within 21 days. After the end of study therapy visit post disease progression, the patient will not be required to return to the clinic for follow-up but will be followed until death by telephone every 3 months to monitor their status.

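### The progression rules for the secondary PFS endpoint contradict each other on T2/FLAIR growth, and two size rules carry the same complete-resection title

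*Combined protocol and SAP*

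**What the plan says.** Section 6.1.1.3 adopts the RANO criteria for high-grade glioma for PFS. It notes that these assess enhancing disease, and adds: "It is likely that a significant number of subjects eligible for the proposed study will have non-enhancing disease". For such patients it says that "the RANO allowance for FLAIR will be utilized for non-enhancing disease", and leaves the detail to the tables that follow.

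**T2/FLAIR growth**
- Section 6.1.1.3.1, Table 3 (first progression, 12 weeks or later), item 4: "For patients receiving antiangiogenic therapy, significant increase in T2/FLAIR non-enhancing lesion may also be considered progressive disease". Items 1 to 3 are a new enhancing lesion outside the radiation field, a rise of at least 25% in the sum of products, and clinical deterioration.
- Section 6.1.1.3.1.1, Table 4, where any one item suffices: "Significant increase in T2/FLAIR non-enhancing lesion on stable or increasing doses of corticosteroids compared with baseline scan or best response after initiation of therapy", provided comorbid events are not the cause.
- Table 5 marks a T2/FLAIR increase with the footnote "Progression occurs when this criterion is present", and any one marked criterion is enough.
- Sections 6.1.1.3.1.2 and 6.1.1.3.1.5 class T2/FLAIR abnormality as non-measurable, make all non-measurable lesions non-target, and count unequivocal non-target progression as progressive disease.
- Section 6.1.1.3.2.4 (after complete resection) does not mention T2/FLAIR.

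**Size after complete resection**
- Table 4, captioned for that setting: "25% increase in sum of the products of perpendicular diameters of enhancing lesions", with an absolute increase of at least 5 mm in a dimension.
- Section 6.1.1.3.2.4, under a section with the same title: "At least a 25% increase in the longest diameter on an axial image of any enhancing tumor", where 5 mm is a minimum size of enhancement and not a minimum growth.

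No section says which rule prevails.

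**The concern.** PFS is a secondary endpoint, compared with the control cohort by a log-rank test (section 10.2.1). Progression is judged locally across 10 to 20 centres, and no central imaging read for PFS is described. Control progression dates come from chart review, and section 9.5 names no definition for abstracting them. If the written rules disagree, two sites can give the same scan different event dates and both follow the protocol.

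The T2/FLAIR conflict concerns a patient type that the protocol itself expects to be common. Prior antiangiogenic treatment is excluded (section 5.2, A), and the protocol regimen of temozolomide plus TTFields contains none. The condition in Table 3 item 4 would therefore ordinarily not be met before first progression.

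Local radiological progression also stops temozolomide (text after Table 4; section 6.1.2.5), so the ambiguity reaches beyond the analysis.

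**Working it through.** The plan has no figure to reproduce here, since no sample size, alpha or power value uses these criteria. The check applies each written rule to the same hypothetical patient or scan.

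**1. FLAIR-only growth.** Assumed: at least 12 weeks after chemoradiotherapy, stable steroids, no new lesion, no change in enhancement, clinically stable, no antiangiogenic therapy.

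| Rule | Result |
|---|---|
| Table 3, item 1 (new enhancing lesion) | not met |
| Table 3, item 2 (sum of products) | not met: section 6.1.1.3 says the criteria assess enhancement, and T2/FLAIR areas are non-measurable |
| Table 3, item 3 (clinical deterioration) | not met |
| Table 3, item 4 (antiangiogenic therapy) | not met |
| Table 4 | progression |
| Table 5 | progression |
| 6.1.1.3.1.5, non-target lesions | progression if unequivocal |
| 6.1.1.3.2.4 | not progression |

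Table 5 has no complete-resection caption, so the conflict with Table 3 remains even if Table 4 is confined to completely resected patients.

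**2. Size rules.** Section 6.1.1.3.2 defines complete resection as residual enhancement under 10 mm. The rules as coded:
- Table 3 item 2: product ratio − 1 ≥ 25%.
- Table 4: product ratio − 1 ≥ 25%, and growth ≥ 5 mm in a dimension.
- 6.1.1.3.2.4: longest-diameter ratio − 1 ≥ 25%, and both measurements ≥ 5 mm.

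Assumed: one enhancing lesion, coronal measurements equal to axial, the finding present on consecutive images, other conditions as in step 1. The sizes are illustrative and do not come from the protocol.

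| Scan (mm) | Product | Longest diameter | Largest growth | Table 3 | Table 4 | 6.1.1.3.2.4 |
|---|---|---|---|---|---|---|
| 8×8 to 9×9 | 81/64: +26.6% | 9/8: +12.5% | 1 mm | yes | no | no |
| 8×8 to 10×10 | 100/64: +56.25% | 10/8: +25.0% | 2 mm | yes | no | yes |
| 9×9 to 12×12 | 144/81: +77.8% | 12/9: +33.3% | 3 mm | yes | no | yes |
| 9×6 to 9×11 | 99/54: +83.3% | 11/9: +22.2% | 5 mm | yes | yes | no |
| 8×8 to 10×6 | 60/64: −6.25% | 10/8: +25.0% | 2 mm | no | no | yes |
| 9×9 to 14×14 | 196/81: +142.0% | 14/9: +55.6% | 5 mm | yes | yes | yes |

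Table 4 and 6.1.1.3.2.4 disagree in both directions: rows 2, 3 and 5 are progression only under 6.1.1.3.2.4, and row 4 only under Table 4. Table 3 has no 5 mm growth condition, so it departs from Table 4 in rows 1 to 3.

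**3. Effect of the 5 mm condition.** For a residual of diameter d < 10 mm growing equally on both axes, Table 4 requires diameter growth of at least 5/d, which exceeds 5/10 = 50%. The product then rises by more than 1.5² − 1 = 125%. Section 6.1.1.3.2.4 needs 25% in diameter, or 1.25² − 1 = 56.25% in product. For equal growth from a small residual, Table 4 is the stricter rule.

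**The case against.** **T2/FLAIR.** Table 3 item 4 is permissive and does not expressly forbid a FLAIR-based call in other patients. Section 6.1.1.3 signals an intention to use FLAIR for non-enhancing disease, and the non-target rule gives a route. This narrows the problem to FLAIR-only growth in a clinically stable patient at first progression; Table 3 does not govern second progression. It does not remove it. Such growth meets no item of Table 3, and the sentence in section 6.1.1.3 is framed around eligibility and defers to the tables that disagree. Section 6.1.1.3.1.5 adds later confirmation by the Study Chair, but does not say which table governs that confirmation.

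**Size.** Table 4 may simply be miscaptioned. It sits under a general response-assessment heading and has a partial-response row, whereas section 6.1.1.3.2.2 says partial response is not assessable without sufficient measurable disease. Section 6.1.1.3.2 also announces modified criteria for minimal residual disease, although it names RECIST and MacDonald and not RANO. This carries weight: if the caption is wrong, the second size rule may be intended, and what remains is a labelling fault.

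**Stronger readings that the documents do not support.**
- From the bare percentages, a reader might infer that the two complete-resection rules differ by more than a factor of two in diameter growth (√1.25 − 1 = 11.8% against 25%), with Table 4 the looser. This omits the 5 mm growth condition, which reverses the order for equal growth from a residual under 10 mm.
- A reader might infer that PFS is delayed in the trial arm relative to controls. That requires sites to follow Table 3 alone and controls to be judged by something looser. No section says either, and section 9.5 refers to a RANO form for controls.

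**Conclusion.** The contradiction on T2/FLAIR stands under either reading of the Table 4 caption. The size conflict stands on the text as written, but may come largely from that caption. The consequence is site-dependent classification of PFS events, of unknown net direction and unknown frequency: the protocol expects a significant number of non-enhancing tumours without giving a proportion, and does not say how many would show FLAIR-only growth. The size examples rest on the illustrative lesions and simplifying assumptions listed with the check; they show that disagreement is possible, not how often it would occur. Overall survival and the Table 10 power do not depend on these criteria. This should be corrected because it affects a secondary comparison between cohorts, but it does not threaten the primary analysis.

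**What to change.** Reconcile section 6.1.1.3, Tables 3, 4 and 5, section 6.1.1.3.1.5 and section 6.1.1.3.2.4 into one progression definition for PFS, or state an explicit order of precedence. Say in one place how T2/FLAIR growth is handled in patients not on antiangiogenic therapy. Correct the Table 4 caption if it is a mislabel; otherwise state which size rule applies to completely resected patients. Add to section 9.5 that control progression dates are abstracted under the same definition.

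Which T2/FLAIR and size criteria to adopt is a clinical decision for the sponsor, particularly as radiological progression stops temozolomide. The statistical requirement is only that there be one rule, applied in both cohorts. The cost is protocol wording and an abstraction instruction, with no added scans. If progression dates have already been entered, those resting on FLAIR-only growth or on a small residual would need rechecking.

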1.3 Schedule of Activities (SoA)

TABLE 1: SCHEDULE OF ACTIVITIES: INTERVENTIONAL SUBJECTS

Study Procedure:	Screening ≤14 days prior to Day 0	Day 0 : Begin TMZ Treatment	Week 4 (-3/+7 days) and every 4 weeks until treatment stop	Week 8 (±7 days) and every 8 weeks only until treatment stop	Progression	After Treatment Stop (Week 4 (+/- 7 days) from end of treatment)	Survival follow-up
Informed Consent	X						
Medical History, Demographics	X						
Medication History	X						
MGMT methylation status	X						
Tumor Tissue Sample ⁹	X				X		
MRI of the brain ¹	X			X	X		
Physical Exam	X		X		X	X	
Neurological status, KPS	X		X		X	X	
CBC w/diff	X ¹⁰		X		X	X	
Pregnancy test (urine or serum)	X ¹⁰						
Biochemistry Panel ⁶	X ¹⁰		X		X	X	
Record Steroid Dose	X		X		X		
Quality of Life Questionnaires ²	X			X	X		
RANO	X			X	X		
Temozolomide Cycle		X ⁷	X ⁸				

Study Procedure:	Screening ≤14 days prior to Day 0	Day 0 : Begin TMZ Treatment	Week 4 (-3/+7 days) and every 4 weeks until treatment stop	Week 8 (±7 days) and every 8 weeks only until treatment stop	Progression	After Treatment Stop (Week 4 (+/- 7 days) from end of treatment)	Survival follow-up
Optune Therapy ⁴		X	X		X		
Optune Compliance ⁴			X				
Adverse Events		X	X	X	X	X	
Concomitant Medications		X	X	X	X	X	
Telephone Interview							X ⁵
DICOM Images shipped for electric fields mapping ¹¹		X			X		X

1) Screening MRI should be done within 21 days of study treatment start. MRI of the brain will be performed routinely at baseline and again every 8 weeks +/- 7 days until treatment termination or second progression, whichever is first. An MRI of the head will be obtained within 21 days in the event of clinical signs of progression. After the post-treatment follow up visit and the patient has not progressed by treatment termination, patient will have contrast-enhanced brain MRI every 3 +/- 1 months for 12 months, then every 6 +/- 2 months for 24 months, then yearly +/- 1 month thereafter or until disease progression, whichever comes first. All MRI scans should be performed with and without contrast and include the scalp.
							

2) Quality of Life will be measured using the EORTC QLQ-C30/BN20 and MMSE every 8 weeks +/- 7 days for the first 2 years then every 3 months thereafter.
							

3) Screening visit should occur within 14 days of adjuvant temozolomide start, with the exception of MRI which can be within 21 days (3 weeks) of adjuvant temozolomide start.
							

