3 OBJECTIVES AND ENDPOINTS

TABLE 2: OBJECTIVES & ENDPOINTS

OBJECTIVES	ENDPOINTS	JUSTIFICATION FOR ENDPOINTS
Primary		
To determine whether TTFIELDS combined with adjuvant temozolomide increases OS in patients with newly diagnosed Grade II and III astrocytoma with TERT promoter mutation only compared to historical and contemporaneous controls.	OS measured in days from Study Day 0 until death. If the study ends and the participant is still living, OS will be measured in days from Study Day 0.	OS remains the primary concern within this patient population. Intent to Treat analysis will be used to determine if this objective is met.
Secondary		

 To determine whether the combination of TTFIELDS and adjuvant temozolomide is safe in the newly diagnosed high-risk Grade II and III astrocytoma. To determine whether TTFIELDS combined with adjuvant temozolomide increases PFS in patients with newly diagnosed Grade II and III astrocytoma with TERT promoter mutation only compared to historical and contemporaneous controls. To evaluate QOL using KPS, EORTC QLQ-C30/BN20, and MMSE in patients treated with TTFIELDS combined with adjuvant temozolomide compared to 	
 PFS measured in days from Day 0 to progression Safety measured by incidence and severity of Adverse Events and Toxicities. Quality of life measured by KPS, EORTC QLQ-C30/BN20, and MMSE Correlation between % Compliance with TTFIELDS and OS 	Safety, Efficacy, and Quality of Life measures for a more complete view of the effects of the study treatment(s).

historical and contemporaneous controls.		
Tertiary/Exploratory		

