5 STUDY POPULATION

5.1 Inclusion Criteria

In order to be eligible to participate in this study, an individual must meet all of the following criteria:

- A. Willing and able to provide written informed consent
- B. Stated willingness to comply with all study procedures and availability for the duration of the study
- C. Male or female, 18 years or older
- D. Life expectancy of at least 3 months
- E. Histologic confirmation of WHO Grade II or III astrocytoma
 - a. mixed oligoastrocytomas are permitted
- F. Mutational identity determined by CLIA-certified sequencing including:
 - a. IDH1/2 wildtype (i.e. lack of detectable mutations on the sequencing report, variants of unknown significance or non-synonymous single nucleotide polymorphisms deviating from wild-type sequence do not apply)
AND
 - b. TERT promoter mutation(s)
- G. Karnofsky performance status $\geq 70\%$
- H. Maximal safe resection
 - a. biopsy alone is allowed
- I. Completed standard chemoradiation with total RT dose of at least 40 Gy and concurrent temozolomide (75mg/m² daily dose with 80% prescribed dose completed)
 - a. Patients with a tumor that was biopsied or resected in the past followed by observation only without definitive chemoradiation and/or chemotherapy given will be eligible, as long as: repeat maximal surgical resection (biopsy only allowed) has been performed, definitive temozolomide/RT treatment meets the criteria above, and adjuvant temozolomide treatment is planned
- J. Candidate for adjuvant high dose temozolomide per investigator's clinical judgement
- K. Adjuvant Temozolomide start date at least 4 weeks, but not more than 6 weeks, from the later of last dose of concomitant temozolomide or radiotherapy
- L. No evidence of early disease progression per RANO criteria at the time of enrollment
- M. Women of childbearing potential (WOCBP) must be using a highly effective method of contraception to

avoid pregnancy throughout the study and for at least 24 weeks after the last dose of study drug to minimize the risk of pregnancy.

- a. Prior to study enrollment, women of childbearing potential must be advised of the importance of avoiding pregnancy during trial participation and the potential risk factors for an unintentional pregnancy.
 - b. Refer to section 10.2.1 for guidance on highly effective contraceptive methods acceptable in this study.

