5.3 Additional Considerations

- Operable patients (biopsy alone allowed) must undergo surgery prior to enrollment.
- All patients must have received radiation therapy with concomitant temozolomide prior to enrollment.
- Patients receiving steroids to control edema may be included in the trial; however, any change in steroid dose must be documented during the follow-up visits.
- Disease status will be determined by comparing screening MRI to the immediate post-surgical MRI. If unavailable, an immediate post-surgical CT can be used for the same purpose.
- Patients who have progressive disease at screening (compared to the immediate post-surgical MRI) are not candidates for this study.
- In the case of local radiological suspicion of pseudoprogression, the patient is still eligible for the study per RANO criteria. However, other imaging modalities (e.g. brain PET, perfusion in addition to T1 weighted MRI) can be obtained to assess biological activity of the tumor if desired but not required by the study.

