Duration of stable disease: Stable disease is measured from the start of the treatment until the criteria for progression are met, taking as reference the smallest measurements recorded since the treatment started, including the baseline measurements.

6.1.1.3.1.8 NEUROLOGICAL EXAM AND PERFORMANCE STATUS

Patients will be graded using the Karnofsky Performance Status scale and their neurological function evaluated as improved, stable or deteriorated in addition to objective measurement of tumor size. These parameters will be used to determine the overall response assessment.

The *Karnofsky Scale* has been adapted for use in many areas, including hospices, cancer clinics, etc., as well as used by various CFS researchers and physicians ([name]; [name]).

The 10-point scale is a quick and easy way to indicate how you are feeling on a given day, without going through several multiple-choice questions or symptom surveys.

TABLE 6: KARNOFSKY SCALE

100	Able to work. Normal; No complaints; No evidence of disease.
90	Able to work. Able to carry on normal activity; Minor symptoms.
80	Able to work. Normal activity with effort; Some symptoms.
70	Independent; not able to work. Cares for self; Unable to carry on normal activity.
60	Disabled; dependent. Requires occasional assistance; cares for most needs.
50	Moderately disabled; dependent. Requires considerable assistance and frequent care.

40	Severely disabled; dependent. Requires special care and assistance.
30	Severely disabled. Hospitalized, death not imminent.
20	Very sick. Active supportive treatment needed.
10	Moribund. Fatal processes are rapidly progressing.

6.1.1.3.1.9 PROGRESSION-FREE SURVIVAL

PFS is defined as the duration of time from start of adjuvant treatment (TMZ C1D1) to time of progression or death, whichever occurs first.

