9.3 Control Cohort Exclusion Criteria

At time of starting adjuvant (first-line) therapy:

- L. Prior treatment with anti-angiogenic agents including bevacizumab.
- M. Progressive disease (according to RANO criteria) after temozolomide/RT, at time of starting adjuvant therapy.
- N. Actively participating in another clinical treatment trial intended to treat the underlying astrocytoma at start of adjuvant Temozolomide treatment.

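### Suspected pseudoprogression that proves to be true progression is back-dated with no floor at Day 0, so PFS can be zero or negative; separately, historical controls may be screened with hindsight

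*Combined protocol and SAP*

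**What the plan says.** **Entry of suspected cases.** Section 5.3: "In the case of local radiological suspicion of pseudoprogression, the patient is still eligible for the study per RANO criteria". On the scan itself, section 1.3 (footnote 1) says: "Screening MRI should be done within 21 days of study treatment start".

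**Dating of progression.** The note under Table 5 (section 6.1.1.3.1.6) concerns uncertainty about pseudoprogression: "Patients may continue on treatment and remain under close observation and evaluation at 4-8 week intervals". If later assessments point to true progression, "then the date of progression should be the time point at which this issue was first raised".

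**PFS origin.** Section 6.1.1.3.1.9: "PFS is defined as the duration of time from start of adjuvant treatment (TMZ C1D1) to time of progression or death, whichever occurs first". Table 2 agrees: "PFS measured in days from Day 0 to progression".

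**Limits on calling progression early.** Table 3 covers the first 12 weeks after chemoradiotherapy. In that period imaging alone can establish progression only through new enhancement outside the radiation field; otherwise histology is needed. Inclusion K puts Day 0 inside that window: "Adjuvant Temozolomide start date at least 4 weeks, but not more than 6 weeks, from the later of last dose" of chemoradiation. Inclusion L and exclusion C bar patients who have already progressed.

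**Controls.** Section 9.2 I requires no early RANO progression when adjuvant temozolomide begins, and 9.3 M excludes "Progressive disease (according to RANO criteria) after temozolomide/RT, at time of starting adjuvant therapy". Section 9.5 takes control data from chart review only, and progression dates are among the items abstracted. Section 9 does not mention suspected pseudoprogression.

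**The concern.** The entry rule, the dating rule and the PFS origin do not fit together. A device patient admitted under 5.3 can later be assigned a progression date before the clock starts, and before a point at which the eligibility criteria say progression had not occurred. The plan has no floor on the date and no rule for non-positive times. In practice someone will either set them to zero, which puts an artificial drop at the origin of the device curve, or drop them, which removes the device arm's earliest progressors. Different sites could date the same history differently.

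The second issue is comparability. Device patients are admitted prospectively, when suspicion is unresolved. For a historical control the outcome of the same suspicion is already in the chart. If the abstractor uses it, early progressors remain in the device arm and disappear from the controls. That would affect the primary OS comparison as well as PFS.

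**Working it through.** **1. The design figure.** Section 10.2 gives one related number: Table 10 power of 0.894 for a 6-month OS gain (90 trial + 90 controls, Weibull shape 2.0, one-sided 0.05).
- Hazard ratio = (22/28)^2 = 0.617; ln = -0.482.
- Event probability = 1 minus mean Weibull survival, with follow-up uniform on 24-60 months: 0.871 at median 22 and 0.751 at median 28.
- Events = 90 x 0.871 + 90 x 0.751 = about 146.
- Schoenfeld power = Phi(sqrt(146/4) x 0.482 - 1.645) = 0.898.

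This agrees with 0.894. Table 10 is not in dispute.

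**2. How far before Day 0 the date can fall.**
- Suspicion on the screening MRI: PFS between 0 and -21 days.
- Suspicion on an earlier post-radiotherapy scan: Day 0 is 28-42 days after chemoradiation ends, so about -42 days at the extreme.

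**3. Consistency of that date with other rules.**

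| Rule | What it implies at the screening scan |
|---|---|
| Note under Table 5 | progression can be dated here once confirmed |
| Table 3 (first 12 weeks) | in-field change on imaging cannot be called progression |
| Inclusion L, exclusion C | the patient has not progressed |
| Section 6.1.1.3.1.4 | target-lesion progression is measured from the smallest on-study sum, baseline included, so a baseline scan cannot be progression against itself |

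**4. Effect on PFS (assumptions).** The documents give neither a frequency nor a PFS assumption for this population. For illustration I used exponential PFS with the medians of the phase 3 glioblastoma trial in section 2.1.2.4 (6.7 and 4.0 months; nominal ratio 4.0/6.7 = 0.597), 90 per arm, affected patients in the device arm only, and 3,000 simulated trials per cell. The first 8-week scan is 56/30.44 = 1.84 months.

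| Affected device patients | Handling | PFS hazard ratio | One-sided power |
|---|---|---|---|
| 0 | - | 0.59 | 0.96 |
| 3 | set to zero | 0.62 | 0.93 |
| 3 | dropped | 0.59 | 0.96 |
| 3 | first 8-week scan | 0.62 | 0.94 |
| 9 | set to zero | 0.68 | 0.83 |
| 9 | dropped | 0.60 | 0.95 |
| 9 | first 8-week scan | 0.66 | 0.87 |

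A separate simulation of the 9-patient case gave 0.675, 0.586 and 0.650, hence the ranges 0.59-0.60 and 0.65-0.66. The dating choice alone (zero versus first scan) moves the ratio by about 0.02. The rest of the shift from 0.59 comes from having early progressors in one arm only. With no true effect and 9 patients set to zero, the one-sided rejection rate falls from about 0.05 to about 0.01.

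**5. Effect on OS, only if matching controls are lost.** OS runs from Day 0 to death, so back-dating changes no OS time. Suppose all matching controls were excluded and the early progressors had a control-treatment median of 8-12 months (both assumed). Power for the 6-month gain would be 0.83-0.86 at 5% affected and 0.74-0.78 at 10%. With the same case mix in both arms it would be 0.89-0.90 and 0.88-0.89.

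**The case against.** **The note may be meant only for on-study scans.** It speaks of patients continuing on treatment, and sits among definitions that count from the start of treatment. That is a fair reading. But a patient admitted under 5.3 who then starts treatment under observation also fits it, and the wording sets no earliest date. The intent may be sound; the rule does not state it.

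**Table 3 and eligibility already block the problem.** In-field change cannot be progression at screening, and section 11.2.2 allows an isodose map to be requested where a lesion may lie outside the field. This shows that the pre-Day-0 date would be wrong. It does not stop the note from producing it, since the note is applied later, after confirmation.

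**A reader might infer that the back-dating rule makes matching controls ineligible.** The documents do not support that. Nothing applies the note to control eligibility. Sections 9.2 I and 9.3 M use nearly the device arm's RANO wording and are anchored at the start of adjuvant treatment. Sections 10.1 and 10.3 tie historical controls to the trial's first-tier criteria and require contemporaneous controls to qualify for the trial. What remains is a risk of hindsight: historical controls are expected to be 60-80 of the 90, the allowance in 5.3 is not repeated for them, first-tier is not defined, and nothing limits the abstractor to what was known at Day 0. The risk is weaker for contemporaneous controls.

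**A reader might also infer that the primary OS result is biased by the dating rule, or that a false benefit could arise.** Neither follows. Back-dating leaves OS untouched, and selective loss of controls would work against the device.

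**The size is assumed.** This stands. The counts, the medians and complete loss of matching controls have no source in the documents.

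**Conclusion.** The PFS dating defect is established from the text: sections 5.3, 6.1.1.3.1.6 and 6.1.1.3.1.9 together permit a progression date before Day 0, in conflict with inclusion L, exclusion C and, for in-field imaging change, Table 3, and with no handling rule. How often this would happen is unknown. At the assumed 9 of 90 the handling choice spans hazard ratios from about 0.59 to 0.68; at 3 of 90 the spread is about 0.03. The effect on this secondary endpoint is modest, but it would be settled after the data are seen.

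The control half is a risk and not a stated rule. If it materialised, OS and PFS would both be biased against the device, and a real benefit could be missed. The OS figures above depend wholly on that assumption. The correction is worth making because it is cheap and removes discretion from an unblinded, non-randomised comparison.

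**What to change.** 1. **Section 6.1.1.3.1.6.** State that back-dating applies only to suspicion first raised on or after Day 0, and that progression is never dated before Day 0. For suspicion already present at screening, date progression at the first post-Day-0 assessment that meets the criteria, keeping the plan's smallest-measurement reference. Reconcile the note with Table 3.
2. **Sections 9.2 I and 9.3 M.** Apply the 5.3 pseudoprogression allowance to controls, and judge their eligibility only on scans and notes dated up to the start of adjuvant temozolomide. Use the same progression-dating rule in both cohorts.
3. **Section 10.2.1.** Add a PFS sensitivity analysis that dates progression at confirmation.

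The cost is a few sentences, an instruction to chart abstractors and one extra analysis. Progression dates move a few weeks later for what is likely to be a handful of patients. Sample size and Table 10 are unaffected, and the changes concern endpoint dating and control selection only.
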